The timeline for follow-up is triggered by the date of the portoenterostomy for subjects with biliary atresia. The surgeon will complete a case report form that describes in detail the surgical findings. The pathologist will detail the pathological findings that are relevant to the diagnosis.

3.A4. In-patient / Discharge

Data will be collected from the time of surgery to the time of discharge.

3.A5. Follow-up

Subjects with biliary atresia will be followed closely during the first year post-portoenterostomy, at 18 and 24 months of age and then annually to 10 years of age or to the time of transplant or death, whichever comes first.

3.A6. Specimen Collection

At baseline and follow up visits, serum, plasma and urine will be collected for the repository. At the time of a liver biopsy, the portoenterostomy and transplant, specimens from the liver, gall bladder, biliary remnant and lymph node may be collected for the repository when the specimens are clinically indicated to be excised and they are not needed for diagnosis.

3.B. Current Outcome of Children with Biliary Atresia Treated at ChiLDREN Centers

One unique feature that is critical to the implementation of controlled clinical studies is the standardization of surgical and medical approaches, which will enable investigators to determine the impact of novel therapeutic interventions (such as this proposed corticosteroid clinical trial) on clinical outcomes across all participating clinical centers. In preparation for this multicenter trial, the DCC carried out a survey among the ChiLDREN clinical centers to determine the outcome of infants with biliary atresia following portoenterostomy during the periods of 1998-2001. This retrospective survey collected data on serum bilirubin levels at 6 months after portoenterostomy and the number of children requiring liver transplantation or dying from a complication of biliary atresia at or before 24 months of age. In total, portoenterostomies were performed on 118 subjects in the 4-year period. Of these, 46% had good bile flow at 6 months after portoenterostomy, and 51% underwent liver transplantation by 24 months of age.

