- Infants with other severe concurrent illnesses such as neurological, cardiovascular, pulmonary, metabolic, endocrine, and renal disorders that would interfere with the conduct and results of the study
- Any other clinical condition that is a contraindication to the use of corticosteroid (e.g., bowel perforation)
- Infants who have received the live attenuated rotavirus vaccine (e.g. Rotateq) within 5 days prior to proposed administration of study drug.

In the unlikely event that the diagnosis of biliary atresia is established during exploratory laparotomy, but the surgeon did not perform a portoenterostomy (as may occur in cases of advanced cirrhosis), the subject will not be eligible for this study.

4.E. Primary and Secondary Outcome Measures

- Primary outcome measure:
Percentage of subjects with serum total bilirubin $<$ 1.5 mg/dL and with native liver at 6 months after portoenterostomy.
- Secondary outcome measures:
All measurements will be made at 12 and 24 months of age (unless noted otherwise):
 1. Serum total bilirubin concentration (and also at 3 months after portoenterostomy)
 2. Survival with native liver at 24 months of age

3. Growth
 - a. Weight for age Z-score (in subjects without ascites)
 - b. Height for age Z score
4. Serum biomarkers of sufficiency of fat-soluble vitamins
 - a. Vitamin A: molar ratio of serum retinol/retinol binding protein
 - b. Vitamin D: serum level of 25-hydroxy vitamin D
 - c. Vitamin E: ratio of serum vitamin E/total lipids
 - d. Vitamin K: International Normalized Ratio (INR)
5. Presence of ascites
- Tertiary outcome measures:

All measurements will be made at 12 and 24 months of age:

 1. International Normalized Ratio (INR)
 2. Serum albumin concentration
 3. Pediatric End-Stage Liver Disease (PELD) score
 4. Platelet count
 5. Serum sodium concentration
 6. Serum bile acid concentrations
 7. Serum concentration of undercarboxylated prothrombin (PIVKA-II)
 8. Head circumference Z-score
 9. Mid-arm circumference and triceps skinfold thickness
 10. Health-related quality of life (HRQOL)
 11. Neurodevelopmental assessment (Bayley score)
 12. Immunologic response to routine childhood vaccination (at 18 months of age)

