5. STATISTICAL ANALYSIS AND DATA MANAGEMENT

5.A. Sample Size

5.A.1. Primary Endpoint

The primary endpoint (Hypothesis 1a) of this clinical trial is whether or not the subject has a serum total bilirubin <1.5 mg/dL with his/her native liver at 6 months after portoenterostomy. To determine the sample size for the clinical trial, we conducted a retrospective study of the level of serum total bilirubin and transplant-free survival in children with biliary atresia treated with portoenterostomy at the 14 ChiLDREN pediatric liver care centers. From the study, 54 of 118 infants (46%) had good bile drainage at 6 months, as determined by a serum total bilirubin level <1 mg/dL. (The results were tabulated at both 1 mg/dL and 2 mg/dL and the results were similar.) Our goal in this trial will be to improve the rate of good bile drainage at 6 months post-surgery from 50% to

75%. Using East-2000® (Cytel Software Company, Cambridge), a total of 110 subjects would need to be randomized to the two treatment groups in order to have 80% power to identify this difference at a 2-tailed 5% level of significance. To allow interim looks at the data after 50% and 75% of the subjects complete the trial using the O'Brien-Fleming spending function, the number of subjects that would be necessary is 114. To compensate for up to 20% attrition; we increased the sample size to a total of 140 subjects; e.g., 70 per group. Attrition will be defined as withdrawal by parents or guardians (which includes subjects who are lost to follow up) occurring within the first 6 months following portoenterostomy (prior to the time of evaluation of the primary outcome measure); however, data from all randomized subjects will be included in an intent-to-treat analysis.

5.A2. Secondary Endpoints

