Hypothesis 1b is that improved bile drainage, as determined by serum total bilirubin with native liver, will be improved in the infants treated with corticosteroids compared to those treated with placebo. Serum total bilirubin concentrations are measured at each clinical visit, including 3 and 6 months after portoenterostomy, and at 12, 18 and 24 months of age. (The time point of 6 months after portoenterostomy is the primary endpoint). A serum total bilirubin value >1.5 mg/dL, transplant or death, is indicative of failure of the portoenterostomy. The time to the first value >1.5 mg/dL (when the value is initially >1.5 and then declines to ≤ 1.5 , the time to the first value >1.5 mg/dL after the decline will be used), to transplant or to death will be considered time to failure of the procedure. The two groups will then be compared by a Cox regression model fitted to the time to failure. Since the test of the primary endpoint is a special case of this analysis, there is greater power for this comparison than for the primary endpoint.

Hypothesis 2 is that survival with native liver at 24 months of age is improved in infants treated with corticosteroids compared to those treated with placebo. In the 118 subjects in our survey of the ChiLDREN centers, 60 (51%) were transplanted by 24 months of age. Similar to the primary endpoint, we will have 80% power to show a 50% improvement in this measure (lowering the transplant rate from 50% to 25%).

Hypothesis 3 is that growth will be improved in infants treated with corticosteroids compared to those treated with placebo. These secondary endpoints, weight for age Z-score (in subjects without ascites) and height for age Z-score, are continuous. Children at the time of portoenterostomy are expected to have normal or near normal growth (mean Z-score near zero). Changes in weight and height Z-scores will be compared between treatment groups. For these endpoints there will be 80% power to identify a difference of 0.55 standard deviations (SD) between groups when 110 subjects are randomized. Since a mean Z-score of -1.0 or less would represent impaired growth and a mean > -0.5 would represent satisfactory growth, there will be almost 80% power to differentiate between these two outcomes.

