Using the same definition of good bile drainage as in the primary hypothesis, the duration of time with good bile drainage (time to onset of poor bile drainage, transplant or death, whichever comes first) will be modeled by Cox proportional hazards model using the same model as above. If there is a statistically significant difference, the profiles of the bilirubin for the two treatment groups will be compared and 95% confidence limits will be computed.

Aim 2: To determine whether corticosteroid treatment after portoenterostomy will improve outcome as defined by survival without transplantation at 24 months of age.

Hypothesis 2: Survival without liver transplantation will be greater at 24 months of age in infants treated with corticosteroids than in those treated with placebo.

A Cox proportional hazards model will be fitted to the time to transplant or death. The same covariates will be included in the model as for the previous hypothesis.

Aim 3: To determine whether corticosteroid treatment after portoenterostomy will improve growth of infants with biliary atresia.

Hypothesis 3: Weight and height Z-scores at 12 and 24 months of age will be higher in the infants treated with corticosteroids than in those treated with placebo.

The weight and height Z-scores at 12 and 24 months of age will each be modeled by a random effects model with the same covariates as above.

Aim 4: To determine whether corticosteroid treatment improves biochemical indicators of each of the fat-soluble vitamins after supplementation with standard doses.

Hypothesis 4a: Treatment with corticosteroids leads to improved bile drainage (hypothesis 1) which, in turn, increases the probability that an infant will achieve vitamin sufficiency of each of the fat-soluble vitamins following supplementation of AquADEK®.

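### Hypothesis 3 (growth) has two outcome definitions, no baseline Z-score in its model, a weight comparison conditioned on ascites, and power wording that is too high at 0.5 and silent on transplant

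*Protocol*

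**What the plan says.** Section 5.A2 of the protocol, under Hypothesis 3, announces a comparison of changes in weight and height Z-scores between arms and states: "For these endpoints there will be 80% power to identify a difference of 0.55 standard deviations (SD) between groups when 110 subjects are randomized". It then takes a mean Z-score of -1.0 or less as impaired growth and a mean above -0.5 as satisfactory growth, and adds that "there will be almost 80% power to differentiate between these two outcomes".

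Section 5.B, Aim 3, describes a different analysis: "The weight and height Z-scores at 12 and 24 months of age will each be modeled by a random effects model". It uses the covariates listed for Hypothesis 1a: treatment, baseline bilirubin, age at surgery, pre-operative complications, sex, race, major anomalies, and site as a random effect. There is no baseline weight or height Z-score, although Table 6 schedules growth measures at recruitment. The general paragraph of 5.B brings in another baseline variable only in a repeat analysis, after a significant imbalance.

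Section 4.E defines the weight outcome as "Weight for age Z-score (in subjects without ascites"). Height carries no such restriction. Hypothesis 5 is that corticosteroids reduce ascites at 12 and 24 months.

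On transplant, the survey in Section 3.B reports that "51% underwent liver transplantation by 24 months of age", and Section 5.A2 plans for a fall from 50% to 25%. The growth paragraph does not mention transplant.

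**The concern.** A change from baseline and an attained Z-score are different outcomes with different variances, so a power stated in SD units does not carry from one to the other. Leaving out the baseline Z-score gives up precision that already collected data would supply.

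The ascites restriction selects infants by their state after treatment began. If corticosteroids reduce ascites as hypothesised, the two arms of the weight comparison are selected differently, and a difference in mean weight could reflect who remains as well as how they grew.

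The power statement matters because a null growth result will be read against it. A reader told that power is 80%, or nearly so, will treat a null as informative. That reading depends on an unstated SD for the second figure and on unstated handling of transplanted infants for both.

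**Working it through.** **Inputs.** Difference 0.55 SD and N = 110, that is 55 per arm (5.A2; the 110 comes from the primary endpoint in 5.A.1). Alpha is taken from the primary endpoint, "at a 2-tailed 5% level of significance", and assumed to apply here. Enrolment is 140, or 70 per arm (5.A.1). Planned transplant by 24 months is 50% versus 25% (5.A2).

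**Formula.** Normal approximation: power = Φ[(δ/σ)/√(1/n₁ + 1/n₂) − 1.96]. The two-sample t-test runs slightly lower and is the figure used below unless stated.

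**1. The plan's own figure.** √(2/55) = 0.1907; 0.55/0.1907 = 2.884; Φ(2.884 − 1.96) = 82.2%. By t-test it is 81.6%. The 80% reproduces; the smallest difference detectable at 80% is 0.54 SD.

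**2. The -1.0 versus -0.5 statement.** With SD = 1, 0.50/0.1907 = 2.622; Φ(0.662) = 74.6%. By t-test it is about 74%. Reaching 80% with 55 per arm needs SD = 0.5/0.534 = 0.94, which the protocol does not state.

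**3. Transplant, if only native-liver infants count at 24 months (an assumption).** From 55 per arm: 0.50 × 55 = 27.5 and 0.75 × 55 = 41.25, taken as 27 and 41. From 70 per arm with no attrition: 35 and 52.5.

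| Starting number | Transplanted by 24 months | n per arm | Power, 0.55 SD | Detectable at 80% |
|---|---|---|---|---|
| 110 | none left out | 55 / 55 | 81.6% | 0.54 SD |
| 110 | 50% vs 25% | 27 / 41 | 59% | 0.69 SD |
| 110 | about 50% in both | 27 / 27 | 51% | 0.76 SD |
| 140 | 50% vs 25% | 35 / 52.5 | 70% | 0.61 SD |
| 140 | 50% in both | 35 / 35 | 62% | 0.67 SD |

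(In the rows with losses, the detectable difference is by normal approximation.) The 20% attrition margin is not meant for this: 5.A.1 defines attrition as withdrawal or loss within 6 months of surgery. The 12-month transplant rate is not given. Assuming 10% to 40% in both arms, native-liver power at 12 months runs from 77% to 60% from 110, and from 86% to 70% from 140.

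**4. Ascites restriction on weight.** The ascites rate is not given. If 10% to 20% of infants in each arm were left out for ascites and none for transplant, 55 per arm becomes 49.5 to 44, and power for 0.55 SD becomes 77% to 72%. The loss of number is secondary; the main point is that the selection happens after randomisation.

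**5. Change, attained value, and attained value with baseline.** Let ρ be the correlation of baseline with follow-up Z-score, with equal SDs. The SD of change is √(2(1 − ρ)); the residual SD with baseline as covariate is √(1 − ρ²). The protocol gives no ρ, so a range is shown, for a difference of 0.55 attained-score SDs at 55 per arm (normal approximation):

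| ρ (assumed) | Change | Attained, no baseline | Attained, baseline as covariate |
|---|---|---|---|
| 0.3 | 68% | 82% | 86% |
| 0.5 | 82% | 82% | 92% |
| 0.7 | 96% | 82% | 98% |

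Change and attained value agree only at ρ = 0.5. Under these assumptions the covariate model has the highest power in every row.

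**The case against.** The strongest reply is that the quoted 80% is correct and that nothing in the protocol limits growth to native-liver infants. Where the protocol wants that limit it says so, as in the primary outcome. Section 6.A3 keeps every subject in the trial to 24 months of age. The phrase "annually to 10 years of age or to the time of transplant or death, whichever comes first" in Section 3.A5 describes the parent database, not this trial. If transplanted infants are measured and included, the 80% stands. This reply holds. A reader might infer from the table that the trial delivers only 51-59% power for growth; the documents do not support that as a fact. What remains is that the stated power depends on handling the protocol leaves open. The rule in 5.B that transplant or death counts as failure does not settle it, because it cannot be applied to a continuous Z-score.

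It can also be said that the 74% assumes SD = 1, that all 140 infants would give about 84%, and that -1.0 or less against above -0.5 makes 0.5 a minimum gap. All true. But the sentence follows directly from the calculation with 110, gives no SD, and at the natural SD of 1 is about six points too high.

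On ascites, the fluid adds weight, so the restriction has a measurement reason, and height is available without it. That justifies reporting the subset; it does not make the subset a randomised comparison.

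On baseline, 5.A2 does use it through the change score, and covariate detail can be left to a statistical analysis plan. But the protocol itself names two different outcomes and fixes a covariate list, so the conflict is already in this document.

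**Conclusion.** The point holds in limited form, on a secondary endpoint.

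- Sections 5.A2 and 5.B define the growth outcome differently, and the listed model omits the baseline Z-score. A reader might take the omission as a source of bias; in a randomised comparison it costs precision only.
- The weight comparison is conditioned on a post-randomisation state that treatment is expected to change. Height is unaffected.
- The 80% for 0.55 SD is not an arithmetic error (81.6% with 110 evaluable). The near-80% for a 0.5 difference is about 74% at 55 per arm and SD 1.
- The growth power is silent on transplant. The figures of 51-59% (from 110) and 62-70% (from 140) at 24 months are conditional on leaving transplanted infants out.

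A reader might go further and conclude that a native-liver comparison would be biased against corticosteroids by a known amount. The direction is plausible if transplant follows severity. The documents give no correlation between severity and growth, so no size can be attached.

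**What to change.** 1. Use one outcome definition in 5.A2 and 5.B: the Z-score at 12 and 24 months, with the baseline weight or height Z-score as a covariate in the main model. The data are already scheduled in Table 6, so the cost is wording.
2. Restate the power for a 0.5 Z-score difference as about 74% with 110 infants at SD 1. Say that the 80% for 0.55 SD assumes transplanted infants are measured and included, and give the lower figures if they are not. The cost is a less favourable statement.
3. Analyse weight in all randomised infants as well as in the ascites-free subset, and do not present the subset as a randomised comparison. The downside is that ascitic fluid adds weight, so height is the cleaner growth measure and should be read first.

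A worst-rank score for transplant or death is not recommended as the main growth analysis. It would turn the growth question largely into Hypothesis 2 and discard any growth measured after transplant. None of the changes needs new data.

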Evaluation	Recruitment or Baseline	Diagnosis/ Surgery/ Discharge	2 wk post	1,2,3 & 6 m post Kasai	12 m age	18 m age	24 m age	At transplant
Windows for visits			±1 wk	±2wks; ±4 wks for 6 m	±1 mo	±2 mo	±2 mo	
Inf. Consent & eligibility	X							
Intake/Medical History	X		X	X	X	X	X	X
Diagnosis and surgery		X						
Discharge Assessment		X						
Medication Record	X	X	X	X	X	X	X	X
Physical Exam, Growth Measures	X	X	X	X	X	X	X	X
Blood tests -Complete blood count -LFTs, PT/INR -Electrolytes, creatinine, BUN, glucose	X	X	X	X	X	X	X	X
Blood tests -Retinol, RBP, 25OH-VitD -Vitamin E, total lipids -Bile acid, PIVKA-II				X*	X	X**	X	
Interval Medical History			X	X	X	X	X	X
Interval Sentinel Events			X	X	X	X	X	X
Neurodevelopmental Assessment (Bayley)					X		X	
Health-Related Quality of Life Inventory (HRQOL)					X		X	
Ophthalmological exam					X			
Antibody titers to vaccines						X		

*Will not be done at the 2 month follow-up, unless a dose adjustment was performed at the 4 week follow-up.

**Will be done only if infant still requires AquADEK® to maintain adequate serum levels of fat-soluble vitamins.

4.I. Surgical procedures and Laboratory Tests

Results of surgical procedure(s) and laboratory tests performed for the initial diagnosis of biliary atresia will be obtained from the medical records. These tests will include hematologic and biochemical analysis (such as complete blood count, liver function tests, prothrombin time/INR, urinalysis, etc), imaging (such as ultrasound examination and hepatobiliary scan), and results of hepatobiliary pathology. Results for tests done at the time of hospital discharge following portoenterostomy will also be obtained from the medical records. Following discharge, the following laboratory tests will be obtained in all subjects, at the time points shown in Table 6, in order to assess study outcomes: liver function tests, complete blood count, vitamin levels and prothrombin time. Serum electrolytes and glucose will also be measured to monitor for potential adverse effects of corticosteroid treatment. These laboratory tests will be performed using standard automated assays in certified clinical laboratories located at each ChiLDREN clinical center.

4.J. Preparation and Administration of Study Medication and Placebo

4.J1. Preparation, Packaging, and Labeling

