- There is a serious adverse event, as outlined in the Data and Safety Monitoring Plan (Section 7).

Any subject who is withdrawn from the study drug/placebo will undergo the drug/placebo taper protocol described in Section 4.F3, and will receive standard medical care.

All subjects will continue to be followed per protocol even if the study drug/placebo is tapered and/or discontinued.

4.L. Retention of Participants

Special effort will be made to keep attrition of study subjects below 20% using the following methods:

- Some of the costs associated with provision of care (such as laboratory tests) will be covered by this study. Thus, we expect minimal attrition due to financial constraints.
- The study coordinator will provide assistance to the parents/legal guardians of study participants, such as scheduling of appointments. Thus, we would make an effort to minimize attrition due to logistical considerations.

4.M. Routine Clinical Care Guidelines for ChiLDREN

Routine clinical care guidelines were established for infants enrolled in the ChiLDREN prospective database and will be followed in this clinical trial. These guidelines were developed based on a consensus of the ChiLDREN clinical investigators in regard to optimal medical and nutritional management and the frequency of follow-up visits for infants with biliary atresia.

4.M1. Frequency of Medical Encounters/Visits

- Enrollment and initial evaluation
- Discharge from the hospital
- 2 weeks postoperative, 1, 2, 3 and 6 months post-operative, and 12, 18 and 24 months of age. The visit at 12 months of age may be combined with the 6-month postoperative visit when the latter is at 10 months of age or greater (which can happen if the portoenterostomy is performed at 4 months of age or later)
- Annually thereafter

4.M2. Physical Exam

At each medical encounter/visit, the following will be obtained:

- Height or recumbent length, weight, head circumference, triceps skinfold thickness, mid-arm circumference.
- Vital signs.
- Skin examination for jaundice, xanthomas, palmar erythema, and vascular pattern.
- Abdomen examination to determine liver size and texture, spleen size, ascites.
- Examination of extremities for edema and clubbing.

4.M3. Diet

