Prior to unmasking the study and the start of any formal analyses, the data for each variable will be examined to identify unusual values that need to be queried, patterns of missing values and whether their distributions are non-Gaussian (i.e., have significant skewness and kurtosis). These analyses are, in general, performed conditional on one or more covariates known to affect the variable being studied; for example, values may be examined conditioned on age of the infant or age at time of portoenterostomy. Data from variables with non-Gaussian distributions will be transformed, if necessary, before building statistical models. Missing data patterns will be examined and, when necessary for the data analysis, missing data may be imputed by appropriate methods depending on the pattern and mechanism of the missing data. Baseline variables will be compared between groups. If a baseline variable is identified as significantly different between groups and it may affect the outcome measure, the analysis of the outcome measure will be repeated with this baseline variable included as a covariate. All models will include clinical site as a random effect.

Aim 1: To determine whether corticosteroid therapy decreases serum bilirubin concentration after portoenterostomy.

Hypothesis 1a: The probability of an infant having good bile drainage at 6 month after portoenterostomy (as defined by a serum total bilirubin level <1.5 ml/dL) will be greater in subjects treated with corticosteroids than in those treated with placebo.

This is the primary hypothesis of this study, upon which the sample size was calculated. A generalized linear model (e.g., a logistic regression model) with random effects will be used to test this hypothesis. The dependent variable is dichotomous: whether the infant has good bile drainage or not; transplantation or death is considered a failure in all analyses. The covariates that will be included in the model are the treatment group, baseline total bilirubin level, age of the infant at portoenterostomy, complications before the surgery, gender and race of the infant, presence of major congenital anomalies, as well as site as a random effect. The test of the primary hypothesis is a test of whether the coefficient of treatment group is zero.

Hypothesis 1b: Improved bile drainage (as defined by a serum total bilirubin level <1.5 mg/dL) will remain for a longer period in infants treated with corticosteroids than in those treated with placebo.

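### Extra adjustment covariates are triggered by baseline significance tests, and the plan does not say that the listed covariate model governs if the repeated analysis disagrees

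*Protocol*

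**What the plan says.** Section 5.B of the protocol opens with general rules for all outcomes. One is "Baseline variables will be compared between groups". The next sentence sets a two-part condition, "If a baseline variable is identified as significantly different between groups and it may affect the outcome measure", and its consequence: "the analysis of the outcome measure will be repeated with this baseline variable included as a covariate".

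The same section then fixes the model for Hypothesis 1a. Besides treatment group and a random effect for site, it contains six baseline covariates: "baseline total bilirubin level, age of the infant at portoenterostomy, complications before the surgery, gender and race of the infant, presence of major congenital anomalies". The primary test is tied to that model: "The test of the primary hypothesis is a test of whether the coefficient of treatment group is zero". Hypotheses 1b, 2 and 3 reuse the same covariates. For Hypothesis 3 the dependent variables are weight and height Z-scores at 12 and 24 months of age, and no baseline Z-score is on the list.

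**The concern.** If randomization has been carried out properly, every baseline difference between the arms is a chance difference, and a significance test of it tests something already known. What makes a covariate worth including is how strongly it predicts the outcome, and the between-arm test does not measure that. The rule can therefore leave out a strong predictor whose imbalance falls just short of significance and bring in a weak one that happens to cross the line.

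The rule also produces a second, data-dependent estimate beside the planned one. Should the two disagree, the reader needs to know which carries the conclusion, and the text does not say so outright. At stake are an avoidable choice after the data are seen and, for some outcomes, the loss of a useful predictor unless a chance p-value admits it.

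**Working it through.** **Why significance is the wrong filter.** For a linear model, leaving out a baseline variable shifts the treatment estimate by about b × d, where b is the variable's effect on the outcome and d is its imbalance between arms. The baseline test looks only at d. With 70 per group (Section 5.A.1), it is significant at two-sided 0.05 when d exceeds about 1.96 × √(2/70) = 1.96 × 0.169 = 0.33 SD. An imbalance just below 0.33 SD in a strong predictor moves the estimate more than one just above 0.33 SD in a weak predictor, yet only the second can trigger a repeat.

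**How often chance alone would flag a variable.** The protocol gives no figure to reproduce, so these inputs are assumptions:

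- Test level: not stated for baseline comparisons. I take 0.05, borrowed from the primary endpoint, which is sized "to identify this difference at a 2-tailed 5% level of significance".
- Number of variables k: not stated, so I use 5 to 30. As a rough guide, Section 4.M2 lists five growth measures ("Height or recumbent length, weight, head circumference, triceps skinfold thickness, mid-arm circumference"). Table 6 lists seven baseline laboratory items: blood count, liver tests, PT/INR and the four in "Electrolytes, creatinine, BUN, glucose". Together that is 12, although several are panels and the liver tests include bilirubin, which is already in the model.

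For independent variables, P(at least one significant) = 1 − (1 − 0.05)^k. For correlated variables I use simulated equicorrelated z-statistics (200,000 draws).

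| k | Independent | Correlation 0.2 | Correlation 0.3 | Correlation 0.5 |
|---|---|---|---|---|
| 5 | 22.6% | 21.8% | 20.9% | 18.2% |
| 12 | 46.0% | 43.0% | 39.6% | 31.8% |
| 14 | 51.2% | 47.5% | 43.8% | 34.9% |
| 30 | 78.5% | 72.2% | 66.2% | 50.5% |

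The level matters as much as k. With k = 14 and independence, a level of 0.01 gives 13.1% and a level of 0.10 gives 77.1%. All these figures precede the condition that the variable may bear on the outcome. If only five variables outside the model pass that filter, the range is 18-23%.

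**Effect on type I error.** I simulated null trials (10,000 per row, n = 140, continuous outcome, first analysis without covariates, repeat adding the significant ones). Here r is the correlation of each variable with the outcome.

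| k, r | First analysis significant | First or repeat significant | Gap |
|---|---|---|---|
| 5, 0.20 | 4.99% | 5.44% | 0.45 points |
| 14, 0.10 | 4.23% | 4.96% | 0.73 points |
| 14, 0.20 | 5.06% | 5.96% | 0.90 points |
| 14, 0.25 | 4.93% | 5.53% | 0.60 points |

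The first column varies around 5% because each entry is a simulation estimate. The gap compares the two analyses within the same trials and is the figure to read. A separate logistic simulation (4,000 null trials per scenario, n = 112, four fixed covariates) agrees: 4.7-5.6% for the fixed model alone and 5.3-6.4% for either. Neither set-up copies the planned model exactly, so these results show order of magnitude only.

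**Where the rule matters.** For Hypotheses 1a, 1b, 2 and 3, imbalance in any of the six listed covariates changes nothing, because they are already in the model. For Hypothesis 3, baseline weight and length are collected (Table 6 and Section 4.M2), but baseline Z-scores are not on the list and would enter only through a chance p-value. Section 5.A2 speaks instead of comparing changes in Z-scores, which would use the baseline value in another way, so the text does not settle the matter. The same gap exists for tertiary outcomes such as platelet count and INR, which Section 5.B says are to be handled in a similar way.

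**The case against.** The best defence is that the plan already does most of what is asked. The Hypothesis 1a model is fixed in advance, its main prognostic covariates enter unconditionally, and the primary test is defined on its treatment coefficient. The general rule says the analysis is repeated, not replaced, which reads most naturally as a supplementary check. The list of baseline variables, the test level and the labelling of the repeat may be in a statistical analysis plan that is not shown. Tertiary outcomes are declared hypothesis-generating in Section 5.A.3, and Hypotheses 4a and 4b regress on bilirubin rather than on treatment arm.

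Much of this stands, and it rules out three stronger readings:

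- A reader might infer that about half of perfectly randomized trials would trigger a repeat. That needs roughly 14 independent tests at 0.05 (ln 0.5 / ln 0.95 = 13.5). The protocol gives neither number, and the figure ignores the second condition.
- A reader might infer a rival result for every outcome. The repeat applies only to outcomes that the variable may affect.
- A reader might infer real damage to the 5% level of the primary test. The gap is below one percentage point and needs an analyst who claims whichever result is significant, which the protocol nowhere permits.

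What the defence does not remove is the trigger. It is a stated rule, not a detail left open, and it selects on the wrong quantity. The repeated model also has a treatment coefficient, and no sentence ranks the two.

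**Conclusion.** The point holds in a limited form. The protocol chooses additional covariates by significance tests between randomized arms, which is a poor criterion, and it does not say explicitly that the listed covariate model governs if the repeated analysis differs. Under the assumptions above (two-sided 0.05, 5 to 30 variables), a chance flag occurs in about 23-79% of trials if the variables are independent and about 18-51% at correlation 0.5, before the relevance condition reduces it. For the primary endpoint the consequence is slight. The rule matters more for outcomes whose own baseline value is off the list, with the growth Z-scores the clearest case. This is a worthwhile improvement and no threat to the trial's main conclusion.

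**What to change.** In Section 5.B (General):

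- Delete the significance-test trigger and report baseline characteristics by arm descriptively.
- State that, for each outcome, the prespecified covariate model is the governing analysis. For Hypothesis 1a this is the model already listed.
- Name any further prognostic covariates on clinical grounds before unmasking, including the outcome's own baseline value where it is collected, such as baseline weight and height Z-scores for Hypothesis 3.
- Label any additional adjusted model a sensitivity analysis.

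The cost is wording only. The main prognostic covariates are already listed, the baseline measurements concerned are already scheduled, and the sample size is unaffected.
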